3.9.2 Concomitant Medications

Prior and concomitant medication use will be recorded for the 4 weeks prior to screening until the final study visit. Antibiotic usage is prohibited during the 14 days prior to study

agent administration (Day 0). Details will include: drug, indication, dose, dose unit, frequency, route, start date and time, stop date and time, ongoing.

Initiation of antibiotic use post-dose will be recorded including name of medication, route, initiation date, and whether the use was based on temperature, investigator's judgment or as per mandated in protocol.

3.9.3 Laboratory Tests

Routine laboratory tests (CBC with differential, serum chemistry panel, CRP, at screening; Day 0; 1 hour and 12 hours post-dose; Days 1 to 7 (24 to 192 hours post-dose); at follow-up weeks 2 and 3 (\pm 1 days) and 4 weeks to 12 months. Assessments taken Days 1 to 7 will be performed once daily beginning 24 hours post-dose. Follow-up assessments 4 weeks to 12 months will occur at 28 days and 2, 4, 8 and 12 months (\pm 2 days) after dosing. Anerobic culture for *C. novyi*-NT) will be performed at above time points except at screening visit.

The results of the CT/MRI scans, tumor biopsy for cultures will be listed by dose level for each patient.

Laboratory tests for magnesium, phosphorous, uric acid and coagulation parameters prothrombin time (PT) and partial thromboplastin time (PTT) will be measured at screening; Day 0; 1 and 12 hours post-dose; Days 1 to 7; at follow-up weeks 2, 3, 4 and months 2, 4, 8 and 12. These laboratory tests will be measured once daily on Days 1 to 7. Laboratory results will be summarized using Systeme International (SI) units, as appropriate.

Category	Parameter
Hematology	Red Blood Cell (RBC),White Blood Cell (WBC) Hemoglobin Mean Corpuscular Volume (MCV), Mean Cell Hemoglobin (MCH), Mean Corpuscular Hemoglobin Concentration (MCHC) Platelet Count, Neutrophils, Lymphocytes, Monocytes Eosinophils, Basophils
Serum Chemistry	Glucose, Uric Acid*, BUN, Creatinine, Calcium, Sodium Potassium, Chloride, Magnesium*, Phosphorous*, CRP*, Total Protein Albumin, Bilirubin, Alkaline Phosphatase, Lactate Dehydrogenase (LDH), Aspartate Aminotransferase (AST) (SGOT), Alanine Aminotransferase (ALT) (SGPT)
Coagulation	Prothrombin time (PT), Partial thromboplastin time (PTT)

Table 3: Laboratory Evaluations

(*) parameters will be measured at specified time points.

3.9.4 Vital Signs

The following vital signs will be measured:

- Blood pressure (systolic and diastolic [mmHg])
- Heart rate (beats per minute)
- Oral Body Temperature (°C)
- Respiratory rate (breaths per minute)
- Body weight

Vital signs will be performed at screening; Day -1 to Day 0 pre-dose; at 15, 30, 45, 60, and 90 minutes post-dose; at 2, 3, 4, 8, 12, 16, 20 hours post-dose; Days 1 to 7 every 4 hours beginning 24 hours post-dose (i.e., at 24, 28, 32, 36, 40, 44, 48...192 hours); days 11, 14, 18, 21, 25 (\pm 1 day); and 28 days (1 month) and 2, 4, 8 and 12 months (\pm 2 days) post-dose.

Weight will be collected at Day -1 to Day 0 pre-dose, Days 7, 14, 21 and 28 and months 2, 4, 8 and 12 post-dose.

3.9.5 Oxygen Saturation by Pulse Oximetry (SpO2)

SpO2 will be performed at screening, Day-1 to Day 0 pre-dose and then continuous monitoring will begin on the day of dosing (Day 0) and continue Days 1 to 7.

3.9.6 Sequential Organ Failure Assessment (SOFA)

A SOFA score assessment will be performed Day -1 to Day 0 pre-dose, at 8 and 16 hours post-dose, and on Days 1 to 7 every 8 hours beginning 24 hours post-dose (i.e., at 24, 32, 40, 48...192 hours). SOFA score will be derived as part of the EDC Process.

3.9.7 Eastern Cooperative Oncology Group (ECOG)

ECOG performance scale status will be performed at screening, Day -1 to Day 0 predose, once daily on Days 1 to 7, days 11, 14, 18, 21 and 25 (\pm 1 day), and 28 days (1 month) and 2, 4, 8 and 12 months (\pm 2 day) post-dose. Each patient's ECOG performance will be graded per the table below:

Table 3: ECOG Performance Status Scale

Grade	ECOG
0	Fully active, able to carry on all pre-disease performance without restriction
1	Restricted in physically strenuous activity but ambulatory and able to carry out work of a light or sedentary nature, e.g., light house work, office work
2	Ambulatory and capable of all self-care but unable to carry out any work

	activities. Up and about more than 50% of waking hours
3	Capable of only limited self-care, confined to bed or chair more than 50% of waking hours
4	Completely disabled. Cannot carry on any self-care. Totally confined to bed or chair
5	Dead

3.9.8 Physical Examinations

Physical examinations will be performed at screening; Day -1 to Day 0 pre-dose; once daily on Days 1 to 7; days 11, 14, 18, 21 and 25 (\pm 1 day); and 28 days (1 month) and 2, 4, 8 and 12 Months (\pm 2 day) post-dose.

3.9.9 Telephone Contact and Survival

Following the inpatient observation period and during the first 28 days post-treatment patients will receive daily phone interviews on the days when they are not scheduled for a clinic visit to evaluate and catalogue any changes in status. These phone interviews will consist of a review of symptoms of infection, temperature checks and compliance with antibiotic regimen.

After patient discontinuation, every effort will be made to collect survival information, including phone calls on a quarterly basis for 12 months to the patient, patient's relatives or primary oncologist.

3.10 Efficacy Assessments

Tumor response and progression will be evaluated using the international criteria proposed by the Response Evaluation Criteria in Solid Tumors (RECIST) Committee (version 1.1: http://www.eortc.be/recist/).

Objective response will be measured by serial CT or MRI scans of the injected tumor and site of metastatic involvement. Overall response, using CT/MRI scan results, will be based on observation of measurable and non-measurable disease as compared to baseline and nadir in target and non-target lesions per RECIST 1.1 at screening and at follow-up times 1 to 12 months post dose.

3.10.1 Tumor Response

3.10.2 Computed Tomography (CT) or MRI Scans

Objective responses will be measured by serial CT or MRI scans of the chest, abdomen, pelvis, and any other sites of metastatic involvement.

CT or MRI scans will be performed at screening, Day 7, and at follow-up times (28 days, and 2, 4, 8 and 12 months post-dose). However, Day 7 CT/MRI is not used for tumor response assessment. It is used for abscess assessment to see if the patient can be discharged.

3.10.3 Response Evaluation Criteria in Solid Tumors (RECIST)

Tumor evaluation per RECIST including targeted injection lesion response and overall response will be evaluated.

Target lesion measurements will be assessed at Screening, and at Months 1, 2, 4, 8, 12. The injection lesion response and overall response will be evaluated at Months 1, 2, 4, 8, and 12.

Target lesion measurements will record the lesion number, location code, description of lesion, evaluation, days after dose administration, date of evaluation, method of evaluation, and the lesions' longest diameter (cm). The tumor response will categorize the lesion response as one of the following: complete, partial, stable, progressive, or unknown.

3.11 Pharmacodynamics - Correlative Studies

Correlative samples will be collected and stored for up to 5 years. Archived tissue (optional) may be used for correlative studies. Serum samples will be collected for banking at screening; Day 0; 1 and 12 hours post-dose; Days 1 to 7; at follow-up weeks 2, 3, 4 and months 2, 4, 8 and 12. Whole blood samples will be collected for immunological assessments and *C. novyi*-NT detection. When performed, post-injection site abscess material samples will be collected and stored (for up to 5 years). Whole blood samples for banking will be taken on Day -1 to Day 0 pre-dose; Days 1 and 7; at weeks 2 and 3; and 28 days (1 month) and 2, 4, 8, and 12 months post-dose. Whole blood samples for immunological assessment will be taken as banking except no collection on day 1. These blood samples will be used to evaluate the following:

3.11.1 Anti-C. novyi-NT Immune and Inflammatory Response

The immune and systemic inflammatory responses during *C. novyi*-NT treatment will be evaluated by serial measurement of CRP, selected cytokines and analysis of selected immune cell populations in blood. C-reactive protein and certain cytokines (IL-6, IL-8, TNF-alpha, etc.) are markers of systemic inflammation. Patient whole blood and serum will be obtained as indicated and, when performed, pre-dose and post-dose tumor samples and abscess material will be collected.

3.11.2 *C. novyi*-NT Detection in Circulation and/or abscess material/postdose tumor sample

Aerobic blood cultures will be taken at screening and Day -1 to Day 0 pre-dose.

Confidential

Page 18 of 35

Anaerobic blood cultures and/or abscess material/post-dose tumor sample (when performed) will be assessed to determine the presence from circulation of *C. novyi*-NT.

Anaerobic blood cultures will be taken on Day -1 to Day 0 pre-dose; 1 and 12 hours postdose; once daily on Days 1 to 7; and at follow-up weeks 2 and 3 and months 1, 2, 4, 8 and 12 post-dose.

Additional aerobic and anaerobic blood cultures may also be performed when clinically indicated.

Tumor biopsy (injected lesion) will be performed on Day -1 to Day 0 pre-dose and tumor biopsy (injected lesion and/or non-injected lesion) will be performed at month 1 (optional) and month 2 (required) post-dose for immunological assessment and tissue banking.

Abscess material post-dose will be collected for culture, immunological assessment and banking, when performed as part of the management of local tumor inflammation and abscessation.

4 STATISTICAL METHODS

4.1 General Considerations

4.1.1 Definition of Analysis Populations

Safety Population

The safety population will include all patients who received any amount of *C. novyi*-NT, the Investigational Medicinal Product (IMP). Patients will be included in the safety analysis according to the dose of IMP received.

Efficacy or Full Analysis Population

The efficacy data set or Full Analysis Set (FAS) will consist of all patients in the safety population who had both, a baseline tumor assessment and at least one post-baseline tumor assessment. Subjects will be included in the efficacy analysis according to the dose of IMP received.

4.1.2 Data Presentations

Data for all enrolled patients who received any amount of IMP will be presented in the data listings. Table summaries will only include those patients that received IMP.

For those listings or data summaries where baseline and change from baseline measurements will be presented, the last observed measurement prior to dosing on Day 0

will be considered the baseline measurement if collecting at both screening and Day -1 to Day 0 pre-dose.

All pre- and post-dose assessments including all unscheduled assessments will be included in the data listings. For pre-dose assessments, the last assessment (including unscheduled) taken for a time point will be used in the data summaries (summary tables, figures, and statistical analysis); for all post-dose time points, the original assessment for any given time point will be used in the data summaries (summary tables, figures, and statistical analysis).

Continuous data will be described using descriptive statistics: number of observations (N), mean, median, standard deviation (SD), minimum and maximum. Frequencies and percentages will be used for summarizing discrete (categorical) data. The denominator for all percentage, unless otherwise specified, will be the number of patients in a given cohort.

Data that are reported as missing will be excluded from all descriptive and nondescriptive data analysis. Observations that are spurious (extreme relative to the majority of the data) will not be altered or removed from any presentation of the data without agreement from the sponsor.

For data listings, all raw data will be reported/displayed exactly as provided. For summaries of quantitative data, the minimum and maximum value will be reported exactly as the raw data are reported; measures of central tendency (means, medians) will be reported to one more decimal place than the raw data; measures of variance (SD) will be reported to two more decimal places than the raw data.

Unless specified otherwise, data collected over time will be listed by cohort, dose level, patient number, and time point (where applicable). Unless specified otherwise, all tables and figures will be presented by dose level. The Summary of Tables, Figures and Listings in the attachment section might be updated later if needed. In this SAP, treatment will refer to any of the following planned categories of *C. novyi*-NT dose level:

- $1 (x \ 10^4 \text{ spores})$
- $3 (x \ 10^4 \text{ spores})$
- $10 (x \ 10^4 \text{ spores})$
- $30 (x \ 10^4 \text{ spores})$
- $100 (x \ 10^4 \text{ spores})$
- $300 (x \ 10^4 \text{ spores})$

4.1.3 **Protocol Deviations**

A protocol deviation is an unplanned excursion from the protocol that is not implemented or intended as a systematic change.

The separate document with detailed criteria and classification of protocol violations and minor deviations will be provided and finalized before database lock. Potential protocol violations will be identified and reviewed prior to database lock. Any modifications to the criteria will be documented after finalization. Every effort will be made to ensure that decisions will not be influenced by dose level to which the patient has been assigned.

Protocol violations will be listed for each dose level. All minor deviations will be listed.

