4.4 Pharmacodynamics Analysis

4.4.1 Anti-C. novyi-NT Immune and Inflammatory Response

All data collected to assess the immune and systemic inflammatory responses during *C. novyi*-NT treatment (CRP, IL-6, IL-8, TNF-alpha, etc.) will be the responsibility of BioMed Valley Discoveries.

4.4.2 *C. novyi*-NT Detection in Circulation and/or abscess material/postdose tumor sample

Results from tumor biopsy assessments will be listed for each patient over time. Information presented will include the date and time of collection, days after IMP administration, anatomical location, and present the following for both anaerobic and aerobic culture: date and time of culture, days after IMP administration, culture results (positive/negative), whether bacteria was found (Yes/No), and if bacteria was found does the bacterial growth represent an infection or contamination.

Results will be summarized to show the number and percentage of patients.

Results from abscess material assessments will be listed for each patient over time. Information presented will include the type of material collected and volume, location (if other, specify non-injected lesion number or anatomical site), days after IMP administration, and present the following for both anaerobic and aerobic culture: date and time of culture, days after IMP administration, the culture result (presence or not), whether bacteria was found (Yes/No), and if bacteria was found does the bacterial growth represent an infection or contamination.

Blood culture and abscess results will be summarized to show the number and percentage of patients with presence of *C. novyi*-NT.

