6.1 Summary of Tables

Patient Dispositi	ion	
Table 14.1.1.1		All subjects
Table 14.1.1.2		
Demographics a	nd Baseline Characteristics	
Table 14.1.2		
Table 14.1.3.1		
Table 14.1.3.2		
Table 14.1.4.1		Safety
Table 14.1.5.1		
6.1.1 M	edication and Treatment	
Table 14.1.6.1	Injection of C. novyi -NT	Safety
Table 14.1.6.2		Safety
Efficacy and Pha	armacodynamics	
Table 14.2.1.1	Number and Percentage of Patients with Non-injected	FAS
	Lesion Measurements	
Table 14.2.1.2	Number and Percentage of Patients with New Lesion Measurements	
Table 14.2.1.3	Summary of Injected Lesion Measurements at Each TimeFASPoint by Each CohortFAS	
Table 14.2.1.4	Summary of Injection Lesion Response	FAS
Table 14.2.1.5	Summary of Overall Lesion Response FA	
Table 14.2.1.6		
Table 14.2.2.1	able 14.2.2.1 Summary of Positive Anaerobic Blood Cultures – Number and Percentage of Patients with Presence of C. novvi-NT	
Table 14.2.2.2		
Table 14.2.2.3 Time (h) of First and Last Positive C. novyi-NT Blood Culture		Safety
Safety		
Table 14.3.1	Overview of Treatment Emergent Adverse Events	
Table 14.3.2		
Table 14.3.3	Treatment-Emergent Adverse Events 'Related to IMP' by System Organ Class, Preferred Term, and Dose Level	Safety

Table 14.3.4	le 14.3.4 Serious Treatment Emergent Adverse Events by System Organ Class, Preferred Term, and Dose Level	
Table 14.3.5	Serious Treatment Emergent Adverse Events 'Related to IMP' by System Organ Class, Preferred Term, and Dose Level	
Table 14.3.6	Summary of AEs Qualified as Dose Limiting Toxicities by System Organ Class, Preferred Term, CTCAE Grade, and Dose Level	Safety
Table 14.3.7	Treatment Emergent Adverse Events 'Related to IMP' by System Organ Class, Preferred Term, CTCAE Grade, and Dose Level	Safety
Table 14.3.8	Treatment Emergent Adverse Events 'Not Related to IMP' by System Organ Class, Preferred Term, CTCAE Grade, and Dose Level	Safety
Table 14.3.9	Treatment Emergent Adverse Events with Frequency >=2 Patients by Preferred Term	Safety
Table 14.3.10	Serious Treatment Emergent Adverse Events by Preferred Term	Safety
Table 14.3.11	Number of Days of Initial Hospitalization	
Table 14.4.1	Shift in Laboratory Hematology from Baseline to each Time Point	
Table 14.4.2	Shift in Laboratory Chemistry from Baseline to each Time Point	Safety
Table 14.4.3		
Table 14.5.1	Shift in Vital Sign from Baseline to each Time Point	Safety
Table 14.5.2		
Table 14.6.1.1	SOFA Scores – Observed Value Summary	Safety

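### The post-dose record rule in SAP 4.1.2, with no exception in 4.4.2, would if read literally drop repeat and arguably between-visit anaerobic cultures from the C. novyi-NT presence and first/last-positive tables

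*SAP*

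**What the plan says.** SAP section 4.1.2 sets three rules on which records are used.

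- **Listings:** "All pre- and post-dose assessments including all unscheduled assessments will be included in the data listings".
- **Pre-dose summaries:** "For pre-dose assessments, the last assessment (including unscheduled) taken for a time point will be used in the data summaries".
- **Post-dose summaries:** "for all post-dose time points, the original assessment for any given time point will be used in the data summaries". The rule is stated to cover summary tables, figures and statistical analysis.

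Section 3.11.2 schedules post-dose anaerobic blood cultures at 1 and 12 hours, then "once daily on Days 1 to 7; and at follow-up weeks 2 and 3 and months 1, 2, 4, 8 and 12 post-dose". It adds: "Additional aerobic and anaerobic blood cultures may also be performed when clinically indicated".

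Section 4.4.2 plans the display: "Blood culture and abscess results will be summarized to show the number and percentage of patients with presence of" *C. novyi*-NT. It has no record-selection rule of its own. Section 6.1 lists Table 14.2.2.1, whose title begins "Summary of Positive Anaerobic Blood Cultures", and Table 14.2.2.3, "Time (h) of First and Last Positive C. novyi-NT Blood Culture". Listing 16.2.5.4 in section 6.3 shows subjects with positive blood cultures.

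**The concern.** Taking one record per time point suits a plot of means over time. It does not suit a patient-level result such as ever positive, first positive or last positive, which needs every record. Section 4.1.2 applies one post-dose rule to all summaries, and nothing in 4.4.2 exempts the culture tables.

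Extra cultures are foreseeable in this design. Section 3.9.1 allows the inpatient stay to be extended while signs of infection resolve, and section 3.9.9 provides telephone review of infection symptoms and temperature on non-visit days up to Day 28.

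Detecting circulating organism is one of the objectives in section 2, and section 3.2 lists blood cultures among both the safety and the pharmacodynamic endpoints. At stake is whether the presence rate and the times of positivity by dose level agree with the data collected. If the rule is not meant literally, the SAP still leaves two programmers free to build different tables from the same data.

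**Working it through.** The SAP gives no rate or other figure on this point, so there is none to reproduce. The check is of the wording, the schedule and the arithmetic of small cohorts.

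**1. Reading the rule.** The pre-dose half of the sentence in 4.1.2 admits unscheduled results and the post-dose half does not. Section 4.5.4, defining the SpO2 baseline, also names repeated or unscheduled evaluations when it wants them. The natural reading of the post-dose half is therefore that later results at a time point are listed but not summarized. For the two kinds of extra culture:

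- *Repeat within a time point* (for example, a second culture on an inpatient day): it is not the original assessment, so the literal rule excludes it.
- *Culture between visits:* it belongs to no visit in the schedule. The rule refers to any given time point and does not say scheduled, so exclusion is an inference.

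**2. Schedule (section 3.11.2).** Post-dose anaerobic cultures: 2 (1 h, 12 h) + 7 (Days 1 to 7) + 2 (weeks 2 and 3) + 5 (months 1, 2, 4, 8, 12) = 16. Gaps are 1 day between Days 1 and 7, then 7 days up to Day 28. At 30.4 days per month they are then about 33, 61, 122 and 122 days. There is room for extra cultures, but the gaps do not show how many would be taken or be positive.

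**3. Hypothetical patients.**

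- *Repeat:* the scheduled Day 3 culture is negative, a second Day 3 culture grows the organism, and all others are negative. Under 4.1.2 the patient is absent from the count in Table 14.2.2.1 but appears in Listing 16.2.5.4.
- *Between visits:* scheduled cultures are positive at 12 h and negative from 24 h on, an extra Day 10 culture is positive, and Day 14 is negative. If the extra culture is excluded, the last positive time is 12 h; if included, 10 × 24 = 240 h.

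**4. Direction.** For each patient, adding records can only turn never positive into ever positive, move the first positive earlier or move the last positive later. A cohort summary of times could move either way, because a newly counted patient also enters it.

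**5. Size of one patient.** The default denominator in 4.1.2 is the number of patients in the cohort, 3 to 6 by section 3.5. One patient is 100/3 = 33.3 points or 100/6 = 16.7 points.

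**6. How often.** This needs two quantities the SAP does not give: *p*, the true ever-positive rate, and *q*, the share of positive patients whose only positive is an excluded culture. The reported rate is then *p*(1 − *q*), and the chance of missing at least one of *n* patients is 1 − (1 − *pq*)^*n*. With *p* assumed at 0.2 to 0.4 and *q* at 0.1 to 0.5:

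| n | p = 0.2, q = 0.1 | p = 0.4, q = 0.5 |
|---|---|---|
| 3 | 1 − 0.98³ = 6% | 1 − 0.80³ = 49% |
| 6 | 1 − 0.98⁶ = 11% | 1 − 0.80⁶ = 74% |

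The width of the range shows that the answer rests almost wholly on the assumptions. It is an illustration, not an estimate.

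**The case against.** The strongest reply is that 4.1.2 only chooses between an original and a repeat at the same time point, and so does not reach a culture taken between visits. Section 4.4.2 supports this: the same sentence summarizes abscess results, which come from samples taken only when a procedure is done and have no scheduled time. A strict scheduled-only rule would leave nothing to summarize there. Table 14.2.2.3 is also a per-patient time in hours, with no limit to scheduled visits in its title. This stands as far as it goes. It makes exclusion of between-visit cultures uncertain, but it does not rescue repeats within a time point.

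Three further replies also stand. Every extra result is in the listings, and infections can be captured as adverse events, so no clinical event is hidden. Only anaerobic extras bear on Table 14.2.2.1, because its title restricts it. And one culture per time point gives patients the same planned number of looks, which is a legitimate reason to keep the rule for by-time-point counts.

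A reader might go further and infer that the plan excludes all clinically indicated cultures, that bacteremia will be under-counted, or that the omitted cultures are the likeliest to be positive and the bias falls mainly after discharge. The SAP does not support this. It never states such an exclusion and gives no positivity rates, and any under-count depends on an extra culture being the sole, first or last positive. Nor can the effect be sized by asking how many hypothetical episodes fall between scheduled visits. That measures gaps in the culture schedule, not the effect of the summary rule.

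**Conclusion.** The point holds in a conditional form. Read literally, section 4.1.2 removes repeat post-dose anaerobic cultures within a time point from Tables 14.2.2.1 and 14.2.2.3. For between-visit cultures the SAP is ambiguous.

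Harm arises only if a removed culture is a patient's only positive, or the first or last. Each patient missed then lowers a cohort's presence rate by 16.7 points (n = 6) to 33.3 points (n = 3), or the patient's first time is too late or last time too early, and the table conflicts with Listing 16.2.5.4. The per-patient size follows from the stated cohort sizes and denominator. The frequency cannot be estimated from the SAP.

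The change is worth making because the tables serve a stated objective and the ambiguity is cheap to remove.

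**What to change.** Add to section 4.4.2, as a stated exception to 4.1.2: patient-level presence of *C. novyi*-NT in blood and the times of first and last positive culture are derived from all post-dose anaerobic blood cultures, scheduled and unscheduled; counts by time point keep the original-assessment rule. Footnote Tables 14.2.2.1 and 14.2.2.3 to match.

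Show the number of post-dose anaerobic cultures per patient with these tables, because patients cultured more often have more chances to be positive. That unequal number of looks is the one real downside.

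The cost is one SAP sentence, footnotes and minor programming. The plan already has unscheduled results collected for the listings, so no new data are needed, and clinical management is unaffected.

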3.7 Blinding

Not applicable. Patients will be enrolled sequentially into a given dosing cohort.

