4.5 Safety Evaluation

4.5.1 Adverse Events (AEs)

Adverse Events will be mapped to the Medical Dictionary Regulatory Activities (MedDRA), Version 14.1 with the lowest level term that most accurately reflects the adverse event.

Adverse events will be categorized as:

- Treatment emergent adverse event (TEAE): A treatment-emergent adverse event is defined as any event not present prior to the initiation of the treatments or any event already present that worsens in either intensity or frequency following exposure to the treatments.
- Non-treatment emergent adverse events (NTEAE): An AE that occurred before the first administration of IMP and did not worsen in severity or frequency after IMP exposure.

All adverse event data recorded on the eCRFs will be listed by dose level and patient. Included on the AE listing will be the adverse event, start date and time, outcome, stop date and time, CTCAE grade, relationship to study drug, action taken, whether the AE was serious, whether TEAE, whether or not a concomitant medication was taken, time of AE onset relative to IMP dosing and AE duration.

All serious adverse events will be listed. A listing of all AEs leading to treatment discontinuation will be presented. Details of death and hospitalization relating to serious adverse events will be listed.

As defined in the protocol, all adverse events will be assigned a CTCAE grade of 1 to 5.

Unless specified otherwise, all adverse event summaries will include the TEAEs only. In these summaries the count of AEs will be the number of patients reporting adverse events and not the number of events reported. If the same AE (preferred term) is reported several times for the same patient, it will only appear once for that specified dose level in the summary tables. For patients with multiple adverse events of the same preferred term and of different intensity, the highest intensity assessment will be used in summaries presented by intensity.

For purposes of the summary tables, AEs will be classified as either being related to IMP or not related. AEs related to IMP will include AEs classified as 'Definite', 'Probable', or 'Possible'. AEs not related to IMP will include AEs classified as 'Not Related' or 'Unlikely'.

Frequency counts will be categorized and displayed by the MedDRA system organ class and preferred term.

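### SAP section 4.1.2 lets individual values be altered or dropped from summary tables and figures for being extreme, with sponsor agreement as the only stated condition

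*SAP*

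**What the plan says.** The rule is one sentence in SAP section 4.1.2. It provides that spurious observations (those that are "extreme relative to the majority of the data) will not be altered or removed from any presentation of the data without agreement from the sponsor". The section gives no threshold for extreme, and it does not say what evidence supports the agreement, when it must be given, or how it is recorded or shown.

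The next paragraph of the section says: "For data listings, all raw data will be reported/displayed exactly as provided". Shortly before, the section says: "All pre- and post-dose assessments including all unscheduled assessments will be included in the data listings".

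On blinding, section 3.7 says: "Not applicable. Patients will be enrolled sequentially into a given dosing cohort". Sections 3.5 and 3.6 set 3 to 6 patients per cohort.

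**The concern.** Spurious ordinarily means not genuine. The SAP supplies its own meaning, which is extreme relative to the rest. A programmer who followed the text could drop or change a true measurement, with sponsor agreement, and comply fully with the plan.

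This matters because the first objective in section 2 is the safety profile, dose-limiting toxicities and maximum tolerated dose. In a small dose-escalation cohort, the patient who reacts is likely to have the values that stand apart from the majority, so the definition can catch the finding the study is looking for. The decision would also be made with the dose level known.

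The SAP is stricter elsewhere. For protocol deviations, section 4.1.3 requires criteria to be final before database lock, later changes to be documented, and every effort to keep decisions free of influence from dose level. None of these safeguards is attached to altering or removing outcome values.

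**Working it through.** The SAP gives no power, alpha or sample-size calculation that this rule could affect, so there is no figure of its own to reproduce. The check is a reading of the text plus simple arithmetic.

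**Inputs from the SAP**
- Cohort size n = 3 to 6 (sections 3.5 and 3.6).
- Percentages use the number of patients in the cohort as denominator unless otherwise specified (section 4.1.2).
- Continuous data are summarised by N, mean, median, SD, minimum and maximum (section 4.1.2).
- A SOFA score above 5 is part of one criterion for dose-limiting toxicity (section 3.1).

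**Input assumed here:** the SOFA totals in step 3. They are not trial data.

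**Step 1. Could a usual numerical rule define extreme within a cohort?** With the value itself included, the largest possible |x − mean|/SD in a sample of n is (n − 1)/√n.
- n = 3: 2/√3 = 1.15
- n = 4: 3/√4 = 1.50
- n = 5: 4/√5 = 1.79
- n = 6: 5/√6 = 2.04

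A 3-SD rule could never flag a value within one cohort, and a 2-SD rule could do so only at n = 6. Within a cohort, extreme is therefore a matter of opinion unless the plan defines it.

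**Step 2. Weight of one patient.** 1/3 = 33.3% and 1/6 = 16.7%. If one patient's shift from normal to high is removed, 1 of 3 (33.3%) becomes 0 of 3, or 1 of 6 (16.7%) becomes 0 of 6. Because the denominator is the cohort size, the result prints exactly like a true zero.

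**Step 3. Effect on a descriptive summary (assumed SOFA totals at one time point).**
- n = 3, totals 0, 1, 8: mean 9/3 = 3.0, maximum 8. Without the 8: mean 1/2 = 0.5, maximum 1.
- n = 6, totals 0, 1, 1, 0, 1, 8: mean 11/6 = 1.83, maximum 8. Without the 8: mean 3/5 = 0.60, maximum 1.

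In both cases the only total above 5 disappears from the summary.

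**Step 4. Which displays are exposed, and would a change show?**
- SOFA descriptive statistics (section 4.5.5) and injected-lesion diameters (section 4.3): a dropped value lowers N, which can be seen. An altered value leaves N unchanged.
- Laboratory and vital signs (sections 4.5.2 and 4.5.3): these sections describe mean-change plots and shift counts. A cohort-size denominator gives no sign of a missing value, and the SAP does not require N to be shown on the plots.
- Listings: if the raw-data sentence governs, the recorded value remains and can be compared with the summary.

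**Step 5. The two sentences side by side.** Taken literally, the clause covers every presentation and hence listings, while the following paragraph says listings show raw data as provided. The second sentence is the more specific and is naturally read as prevailing. The mismatch is then minor, and the clause acts on tables and figures.

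**The case against.** The sentence makes retention the default. Strictly, it states a necessary condition for change, probably as a limit on the programmers, and does not tell anyone to delete real data. Query and source-verification procedures may well stand in the protocol or in data-management documents that are not at hand. That is fair, and the absence of such procedures from the SAP is not the fault. The fault is that the SAP redefines spurious as extreme and names sponsor agreement as the one condition, without tying it to any verified error.

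A reader might infer that the patient with severe toxicity could be taken out of the safety displays. The SAP does not support this. The clause acts on observations, not patients, and section 4.1.1 has no exclusion for extreme values: "The safety population will include all patients who received any amount of" study agent. Section 4.5.1 adds: "All adverse event data recorded on the eCRFs will be listed by dose level and patient". All serious adverse events are listed as well. Under section 3.9.1, Grade 3 and 4 laboratory results that worsen from baseline are reported as adverse events, so they reach the adverse-event outputs whatever happens to a laboratory mean.

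A reader might also infer that dose-limiting toxicity counts or escalation could be affected. The clause is broadly worded and does not expressly exempt adverse-event tables, but nothing in the SAP applies it to those counts or decisions.

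Nor would a removal be invisible. Raw listings, the N in descriptive tables, and the listing of derived data under section 4.6 give a careful reader the means to find it. What is missing is any requirement to flag it.

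Finally, the direction of bias is not fixed. Dropping a high toxicity value makes a dose look safer. Dropping a large lesion increase makes it look more active, and dropping a large shrinkage does the reverse.

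**Conclusion.** The point holds for individual values in summary tables and figures. As written, the SAP permits a genuine extreme laboratory, vital-sign, SOFA or lesion value to be altered or left out on sponsor agreement alone, in an unblinded study where one patient is 16.7% to 33.3% of a dose level. In the assumed examples the cohort mean falls from 3.0 to 0.5 (n = 3) or from 1.83 to 0.60 (n = 6), and the maximum from 8 to 1.

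These sizes rest on assumed scores and show what the rule could do, not what was done. The conclusion does not extend to the safety population, the adverse-event and raw-data listings, or dose-escalation decisions. Because those safeguards stand, this is a low-cost improvement to the wording and does not undermine the study's main safety conclusions.

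**What to change.** Replace the sentence in section 4.1.2 with:

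> No recorded value is altered or removed from any table, figure or listing because it is extreme. Implausible values are queried and corrected only in the clinical database, before lock, with source confirmation and audit trail. If a value remains in dispute, the main display keeps it, and a footnoted display without it may be added beside it.

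This also brings the clause into line with the raw-data rule for listings. The cost is a change of SAP wording, with no new data, patients or analyses. The downside is that a real error that cannot be resolved against source stays in the main display with a footnote. In cohorts this small, that is easier to explain than a summary from which a value has been dropped.
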